## **7.2 Drug Orders, Transfers, Returns, and Accountability**

The Investigator, or a responsible party designated by the Investigator, must maintain a careful record of the inventory and disposition of all drugs received using the NCI Oral Drug Accountability Record Form (DARF) (available on the CTEP home page (<http://ctep.cancer.gov>)). The DARFs document the drug delivery date to the site, inventory at the site, use by each study participant. Store and maintain separate NCI Investigational Agent Accountability Records for each agent, strength, formulation and ordering investigator on this protocol. The investigator will ensure that the drugs are used only in accordance with this protocol.

Drug will be shipped through a third party vendor. Instructions for drug ordering are available on the AMC website ([www.AIDSCancer.org](http://www.AIDSCancer.org)).

## **8.0 CLINICAL AND LABORATORY EVALUATIONS**

Schedules shown in the Study Calendar below are provided in [Appendix I](#).

### **8.1 Screening Evaluations**

Screening evaluations are used to determine eligibility and are to be conducted within 21 days before treatment segment enrollment, unless otherwise specified. Participating sites must ensure a participant meets all eligibility criteria before completing the protocol-specific eligibility checklist in Advantage eClinical.

- 8.1.1 Informed consent must be collected prior to performing any screening evaluations.
- 8.1.2 Medical history, including history of AIDS-defining illnesses, history of smoking and current tobacco use, performance status, life expectancy, any prior receipt of thalidomide or its analogs, history of other malignancies, history of major cardiovascular events, history of coagulation disorders per [Section 3.2.13](#), and participant demographic information.
- 8.1.3 Medication history, including all current ART and prior ART regimens. Per [Section 3.1.8](#) the ART regimen must be stable for 12 weeks prior to study enrollment. All prescription and non-prescription medications, including over-the-counter medications, alternative therapies, herbal medicines/tea, and dietary supplements taken within 14 days prior to study enrollment must be recorded.
- 8.1.4 Complete physical examination including vital signs, height, weight, assessment of signs and symptoms,, neuropathy evaluation (i.e., pain, aching, or burning in hands or feet), and performance status.
- 8.1.5 Biopsy diagnostic of KS at any time prior to study enrollment. The biopsy specimen must be available for review (including performing or reviewing latency-associated nuclear antigen (LANA) stains) and confirmation by an AMC-approved pathologist. Specimens for this review must conform to the requirements listed in [Appendix V](#).
- 8.1.6 Tumor assessment to determine that participant does not have visceral disease requiring cytotoxic chemotherapy.
- 8.1.7 HIV plasma quantitative RNA viral load via HIV quantitative polymerase chain reaction (PCR) within 12 weeks of enrollment.
- 8.1.8 Chest X-ray (CXR) to evaluate for pulmonary KS. If available and clinically indicated, computed tomography (CT) of the lung may be performed to verify chest X-ray findings.
- 8.1.9 Pregnancy testing if FCBP by beta-human chorionic gonadotropin (b-HCG) with a sensitivity of at least 25 mIU/mL within 14 days prior to enrollment.
- 8.1.10 Complete blood count (CBC) with differential and platelets within 7 days prior to enrollment.
- 8.1.11 Serum chemistries including sodium, potassium, chloride, bicarbonate, phosphate, glucose, creatinine, albumin, AST, ALT, alkaline phosphatase, and total bilirubin within 7 days prior to enrollment.

## **8.2 Baseline Evaluations**

Baseline evaluations are to be conducted within 7 days prior to starting treatment, unless otherwise specified below. In the event that the participant's condition is deteriorating, laboratory evaluations should be repeated within 48 hours prior to initiation of the first cycle of therapy.

- 8.2.1 Enrollment into Advantage eClinical Treatment Segment once all eligibility criteria are confirmed.
- 8.2.2 Interim medical history, including HIV-related and AIDS-defining events.
- 8.2.3 Review of concurrent medications as defined in [Section 8.1.3](#).
- 8.2.4 Complete physical examination including vital signs, weight, assessment of signs and symptoms, neuropathy evaluation (i.e., pain, aching, or burning in hands or feet), and performance status.
- 8.2.5 Tumor assessments with photographic record must be performed prior to initiating treatment. These may be performed on Day 1, but no earlier than 7 days before initiating study treatment. If the screening tumor assessments with photographic record are performed within 7 days before initiating study treatment, the screening tumor assessments can be used as a baseline assessment. Tumor assessments and photographs should be performed as outlined in the KS Tumor Assessment MOP.
- 8.2.6 Staging criteria: KS staging will be based on the modified AIDS Clinical Trials Group (ACTG) Oncology Committee Staging Criteria as outlined in [Appendix XIII](#).
- 8.2.7 HIV plasma quantitative RNA viral load via HIV quantitative PCR within 28 days before initiating study treatment. If the HIV viral load used to determine eligibility is performed within 28 days of the start of protocol therapy, the screening viral load can be used as a baseline test. The results of the baseline HIV viral load do not need to be available prior to the start of protocol therapy.  
A CD4 T cell count is required within 28 days prior to study treatment.
- 8.2.8 Pregnancy prevention counseling for all participants before starting each new cycle of pomalidomide, as required at [Appendix VII](#). Pregnancy testing if FCBP by b-HCG with a sensitivity of at least 25 mIU/mL within 24 hours of starting pomalidomide.
- 8.2.9 Whole blood collection for serum cytokine studies (one 7 mL red top tube) ([Appendix XII](#)) on day 1 prior to the first dose.

## **8.3 Evaluations During Treatment**

Except as noted, evaluations required to ensure safe and timely treatment may be conducted within three days prior to beginning cycles 2-12 of pomalidomide.

- 8.3.1 KS Tumor Assessment will be performed prior to every cycle.
  - 8.3.2.1 For participants with known pulmonary KS at study entry, a CXR (and CT scan, if available and clinically indicated) will be repeated every third cycle.
  - 8.3.2.2 If during the pre-treatment assessment at cycle 7 day 1 the participant has

stable disease (SD) or progressive disease (PD) the participant must discontinue treatment. If the participant has a partial response (PR) or a complete response (CR), the participant may continue with treatment for up to 12 cycles.

- 8.3.2 Photographic documentation will be completed at each visit when the KS response category changes (see KS Tumor Assessment MOP for lesion photography guidelines).
- 8.3.3 Complete physical examination including vital signs, weight, assessment of signs and symptoms and toxicity, neuropathy evaluation (i.e., pain, aching, or burning in hands or feet), and performance status.
- 8.3.4 Interim medical history, including HIV-related and AIDS-defining events.
- 8.3.5 Assessment of adherence to ART (by participant report of missed doses).
- 8.3.6 Assessment of adherence to study therapy.
- 8.3.7 Review of concurrent medications.
- 8.3.8 CBC with differential and platelets.
- 8.3.9 Serum chemistries: sodium, potassium, chloride, bicarbonate, phosphate, glucose, creatinine, albumin, AST, ALT, alkaline phosphatase, and total bilirubin.
- 8.3.10 HIV plasma quantitative RNA viral load via HIV quantitative PCR, and CD4 T cell count prior to cycles 2, 4, 7, and 10.
- 8.3.11 Pregnancy prevention counseling for all participants before starting each new cycle of pomalidomide, as required at [Appendix VII](#). Pregnancy testing if FCBP by beta-HCG with a sensitivity of at least 25 mIU/mL within 24 hours of starting each cycle of pomalidomide. Weekly pregnancy testing for FCBP is required during the first cycle. If menstrual cycles are irregular, the pregnancy testing must occur weekly for the first 28 days and then every 10-14 days while on study.
- 8.3.12 Whole blood collection for serum cytokine studies (one 7 mL red top tube) prior to treatment for cycle 3 day 1 and cycle 7 day 1 ([Appendix XII](#)).

## **8.4 Treatment Discontinuation Evaluations**

- 8.4.1 Participants who complete all treatment per-protocol or who discontinue protocol treatment early for any reason should have the following evaluations and laboratory tests within 1 week and again at 30 days ( $\pm 7$  days) after the last dose of protocol treatment, unless otherwise noted.
  - 8.4.1.1 KS tumor assessment, including re-evaluation of visceral disease if not already done while on study, and photographic documentation.
  - 8.4.1.2 Complete physical examination including vital signs, weight, assessment of signs and symptoms and toxicity, neuropathy evaluation (i.e., pain, aching, or burning in hands or feet), and performance status.
  - 8.4.1.3 Interim medical history, including HIV-related and AIDS-defining events.

- 8.4.1.4 Assessment of adherence to ART.
- 8.4.1.5 Assessment of adherence to study therapy.
- 8.4.1.6 Review of concurrent medications.
- 8.4.1.7 CBC with differential and platelets.
- 8.4.1.8 Serum chemistries: sodium, potassium, chloride, bicarbonate, phosphate, glucose, creatinine, albumin, AST, ALT, alkaline phosphatase, and total bilirubin.
- 8.4.1.9 HIV plasma quantitative RNA viral load via HIV quantitative PCR, and CD4 T cell count within 1 week of last dose of protocol treatment.
- 8.4.1.10 CXR (and CT if available/indicated) for participants who had either an abnormal CXR/CT at Screening or have clinical evidence for new pulmonary involvement. CXR/CT should only occur once following the last dose of protocol treatment.
- 8.4.1.11 Pregnancy testing if FCBP by beta-HCG with a sensitivity of at least 25 mIU/mL at study discontinuation, and at Day 28 ( $\pm 7$  days) following study drug discontinuation. If menstrual cycles are irregular, the pregnancy testing must occur at study discontinuation, and again at 14 and 28 days ( $\pm 7$  days) after this date.
- 8.4.1.12 Participants who discontinue treatment will have whole blood collection for serum cytokine studies (one 7 mL red top tube) within 1 week of last dose of protocol treatment ([Appendix XII](#)).
- 8.4.1.13 Participants with stable disease (SD) or progressive disease (PD) at the time of treatment discontinuation will complete all study follow up at the 30 day post-treatment visit and the Off-Study Summary Form will be completed. See [Section 6.4.2](#) for the timeline for routine adverse event reporting.

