### **4.5 Duration of Follow Up**

Participants with complete response (CR) or partial response (PR) will be followed for up to 48 weeks after their last dose of study treatment or until PD or death, whichever occurs first, for safety and response duration ([Section 8.4](#)). Participants with stable disease (SD) or progressive disease (PD) will be followed for 30 days after treatment discontinuation.

Participants removed from study treatment for unacceptable adverse event(s) will be followed at least weekly until resolution or stabilization of the adverse event, after which they will be followed according to their response status.

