## 8.5 Follow-up Evaluations

Only participants who achieve PR or CR will have additional physical examinations repeated every 12 weeks (counting from the last day, Day 28, of the final cycle,  $\pm 2$  weeks) for up to 48 weeks or until an earlier time of PD requiring additional treatment. AEs must be reported if the AE began any time within 30 days of completing study treatment. Additionally, if a site learns of any occurrence of death, cancer or fetal anomaly that is possibly, probably, or definitely related to the drug at any time after the study is closed, the event should be reported to the AMC through Advantage eClinical within 24 hours of when the investigator learns of the event.

The following procedures should be performed during the follow-up visits:

- 8.5.1 Complete physical examination including vital signs, signs and symptoms review, toxicity, neuropathy evaluation (i.e., pain, aching, or burning in hands or feet), and performance status.
- 8.5.2 Review of interim medical history, including AIDS-defining events.

8.5.3 KS tumor assessment.

8.5.4 At a participant's final study visit, the Off-Study Summary Form will be completed.

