- A 50% or greater decrease in the number or size of all measurable oral or visceral lesions lasting for at least 4 weeks, without evidence for progression of cutaneous lesions; OR
- Complete disappearance of non-measurable oral or visceral lesions lasting for at least 4 weeks, without evidence for progression of cutaneous lesions.

NOTE: To classify a response as PR, the participant must have at least a PR in either the cutaneous or noncutaneous sites of disease, and no evidence of progression as defined in the above criteria.

NOTE: Participants with residual tumor-associated edema or effusion who otherwise meet the criteria for CR will be classified as having a PR.

9.1.3 Stable disease (SD) is defined as any response not meeting the criteria for CR, PR, or PD.

9.1.4 Progressive disease (PD) is defined as follows:

*For participants with  $\leq 50$  cutaneous lesions*

PD is defined as any one or more of the following:

- $\geq 25\%$  increase in the area of the cutaneous marker lesions compared to entry or best response;
- $\geq 25\%$  increase in the total lesion count, or a minimum of five new lesions, whichever is greater, compared with entry or best response;
- $\geq 25\%$  increase in the number of raised lesions, or a minimum of five new raised lesions, whichever is greater, compared with entry or best response.

NOTE: There are body sites where disease is particularly difficult to evaluate, and a few new lesions may be counted in spite of the fact that a participant is not actually progressing. For example, lesions of the foot, particularly those that are flat, are difficult to evaluate because their intensity may vary based on how much edema is present, how much the person walked the day before, how long his/her feet have been in a dependent position prior to the physical exam.

*For participants with  $> 50$  cutaneous lesions*

PD is defined as any one or more of the following:

- $\geq 25\%$  increase in the area of the cutaneous marker lesions compared to entry or best response;
- $\geq 25\%$  increase in the total number of lesions in the prospectively defined anatomic sites containing representative lesions;
- a total of five new lesions in anatomic sites that were previously documented as having no evidence of cutaneous disease,

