9.1.9 Response duration

Response duration is defined as the time from first documentation of response to documentation of first progression.

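### Sections 8.4.1.13 and 8.5 give conflicting follow-up to a participant whose response has lapsed to stable disease by the end of treatment, which can bias response duration

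*Combined protocol and SAP*

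**What the plan says.** Two sections decide who stays in follow-up after treatment, and they use different criteria.

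- **Section 8.4.1.13** goes by status when treatment stops. Participants in SD or PD "at the time of treatment discontinuation will complete all study follow up at the 30 day post-treatment visit", and the off-study form is then completed.
- **Section 8.5** goes by response achieved: "Only participants who achieve PR or CR will have additional physical examinations repeated every 12 weeks", for up to 48 weeks. KS tumor assessment is part of each visit.

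Three other places leave the question open. Section 4.5 says that participants with CR or PR are "followed for up to 48 weeks after their last dose of study treatment or until PD or death, whichever occurs first", and gives safety and response duration as the purpose. Its second sentence reads: "Participants with stable disease (SD) or progressive disease (PD) will be followed for 30 days after treatment discontinuation". Appendix I note n and the synopsis also refer to participants with, or showing, CR or PR. None of the three says whether best response or current status is meant.

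Two definitions matter. Section 9.1.3 makes SD a residual category: "Stable disease (SD) is defined as any response not meeting the criteria for CR, PR, or PD". Section 9.1.9 makes progression the event: "Response duration is defined as the time from first documentation of response to documentation of first progression".

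The end of follow-up is also worded in more than one way. Section 4.5 and Appendix I note n stop at PD (4.5 adds death), whereas 8.5 continues "until an earlier time of PD requiring additional treatment".

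**The concern.** A participant who reached a confirmed PR, lost it, and has not progressed falls under both rules when treatment stops. Section 8.3.2.2 can produce this case, because a participant found in SD at the assessment before cycle 7 (C7D1) must discontinue. Section 8.4.1.13 then closes the participant's follow-up at 30 days, while 8.5 keeps the same participant for up to 48 weeks. Two sites could treat identical participants differently.

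At stake is response duration. If 8.4.1.13 is followed, the responders who leave early are those whose disease has begun to regrow. Their censoring is therefore related to their risk of progression, and a standard estimate that treats it as non-informative would tend to be too long. Section 2.2.1 lists the inability to evaluate the duration of unmaintained remission as a limitation of the earlier pomalidomide trial in KS, so the observation time at issue is time that this trial has reason to want.

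**Working it through.** The plan states no figure for this point, so there is none to reproduce. The check has three steps.

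**1. Can a responder be in SD under the protocol's own thresholds?**

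Inputs from Section 9.1, marker-lesion area with entry = 100:
- PR needs a decrease of at least 50% from entry, so it is lost when area > 50.
- PD needs an increase of at least 25% over entry or best response. Taking best response as the reference, PD is reached when area ≥ 1.25 × best.
- SD by area is therefore 50 < area < 1.25 × best. This window exists only if 1.25 × best > 50, that is, best > 40.

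| Best area (% of entry) | PD reached at | SD window after PR |
|---|---|---|
| 50 | 1.25 × 50 = 62.5 | 50 to 62.5 |
| 45 | 1.25 × 45 = 56.25 | 50 to 56.25 |
| 42 | 1.25 × 42 = 52.5 | 50 to 52.5 |
| 40 | 1.25 × 40 = 50 | none |
| 30 | 1.25 × 30 = 37.5 | none; PD comes before PR is lost |

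Example: best 50, now 55. The decrease from entry is 45%, so PR by area is lost. The rise over best is (55 − 50)/50 = 10%, so there is no PD by area. If no other PR or PD criterion is met, Section 9.1.3 makes this SD.

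The count criterion (50 lesions or fewer) can also leave a window, because PD needs a rise of at least 25% or five lesions, whichever is greater. With 20 lesions at entry and 10 at best, 25% of 10 is 2.5, so five applies and PD starts at 15. Counts of 11 to 14 lie in between. This works only if lesions present at entry return, because the PR count criterion refers to those lesions. New lesions alone would not cancel it.

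**2. Which rule applies to that participant?**

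| Place | Basis | Lapsed PR, now SD |
|---|---|---|
| 8.4.1.13 | status at discontinuation | off study at 30 days |
| 8.5 | response achieved | up to 48 weeks (336 days) |
| 4.5, first sentence | with CR or PR; no time point | unclear |
| 4.5, second sentence | with SD or PD; no time point | 30 days if current status is meant |
| Appendix I note n | with CR or PR; no time point | unclear |

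The direct conflict is 8.4.1.13 against 8.5.

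**3. How many participants could be affected?**

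Responders = 26 × response rate. At the 30% design alternative this is 7.8, about 8, and each responder is 1/8 = 12.5% of the response-duration data. The range is 2.6 at the 10% null rate and 19.0 at the 73% reported for the earlier trial (Section 2.2.1). The share of responders in SD at discontinuation is not given and can be zero.

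To show the possible size, assume 8 responders and start the clock at discontinuation. Let k responders be in SD at that point and progress 12 weeks later, while the others stay free of progression. The proportion free of progression at 24 weeks is (8 − k)/8 under 8.5. Under 8.4.1.13 it is 100%, because all k are censored first.

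| k | Under 8.5 | Under 8.4.1.13 |
|---|---|---|
| 0 | 100% | 100% |
| 1 | 87.5% | 100% |
| 2 | 75% | 100% |
| 3 | 62.5% | 100% |

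Section 9.1.9 starts the clock at first response, not at discontinuation. On that clock the two rules separate later, and at 24 weeks they may not differ at all for participants who responded early.

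**The case against.** The strongest reply is that the conflict rests on one word in 8.5, *achieve*, and that the other passages can be read as going by status at discontinuation. A second reply is that 9.1.9 runs response to first progression, so a responder without PD might be regarded as still in response. On that reading the two sections agree. Neither reply settles the matter. No passage says that a former responder keeps the PR label, and 9.1.3 makes SD whatever is not CR, PR or PD. Section 8.3.2.2 also stops treatment on the status found at C7D1.

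Several limits do stand:
- **Section 4.5 is not a clean counter-rule.** A reader might infer from its first sentence that it contradicts 8.4.1.13. Its second sentence gives SD and PD the same 30 days.
- **Loss of PR is not failure of response.** A reader might infer that participants are censored at the moment the response fails. Under 9.1.9 the event is progression. Tumor assessment is still done within 1 week and again at 30 days after the last dose, so early PD is recorded. A responder in PD at discontinuation already has the event.
- **The group is narrow.** Every PR route must be lost (count, flattening, area, oral or visceral), and by area there is no SD window once the best decrease is 60% or more.
- **Response duration is not a listed endpoint** in Section 10.1, and 10.1.4 gives no analysis or censoring rule for it.
- **The difference in how PD is worded** as the end of follow-up does not change response duration, which stops at first progression in any case. It is a point of consistency only.

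**Conclusion.** The conflict between 8.4.1.13 and 8.5 is real, and the protocol's own response criteria allow a participant to meet both. If 8.4.1.13 is applied, lapsed responders without PD have about 30 days of observation after treatment instead of up to 48 weeks. Their censoring is likely to be informative, and response duration would tend to be overstated.

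The size cannot be fixed from the documents. It concerns an unknown, possibly empty, subset of about 8 responders, assuming a 30% response rate in 26 participants. The direction of bias assumes that lapsed responders progress sooner than the rest and that the analysis censors them at their last assessment.

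A reader might infer that the trial's main conclusion is at risk. It is not: overall response rate, complete response rate and the Grade 3 or higher toxicity proportion do not depend on this follow-up. The point is worth acting on because 4.5 names response duration as a purpose of the 48-week follow-up and the repair is cheap.

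**What to change.** 1. Reconcile 8.4.1.13, the second sentence of 4.5, 8.5 and Appendix I note n around one criterion. Any participant who achieved CR or PR at any time and has no documented PD stays in the 12-weekly follow-up. The 30-day follow-up applies to those who never responded or who have documented PD.
2. Use one end of follow-up in all of these places: documented PD, death or 48 weeks, whichever is first.
3. Add a censoring rule for response duration to 10.1.4, and report how many responders were in SD at discontinuation.
4. Enrollment was planned to close at the end of 2023 (10.1.2), so some participants may already have left under 8.4.1.13. For them, add a sensitivity analysis of response duration in which lapse to SD counts as the end of response.

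The cost is amendment wording, one short additional analysis, and at most 48/12 = 4 extra visits for each affected participant.
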